Both the frequency of WP use and the manner with which it is smoked contributes to the development and maintenance of nicotine dependence.⁹⁻¹¹ WP smoking delivers pharmacologically active doses of nicotine to the user.^{12,13} Although most WP smokers in the U.S. smoke WP intermittently, some eventually move on to more frequent use.^{14,15} **If flavorings are determined to influence users to initially try WP, improve their perceived satisfaction from use of the product, and/or make it more palatable to puff more frequently or take longer/deeper puffs, then they would be contributing to the initiation and maintenance of WP dependence.** Moreover, current level of WP dependence may moderate the impact of flavorings on smoking patterns. Unflavored WP tobacco is more difficult to find and purchase, and internet customer reviews suggest that few WP users try and even fewer continue to use unflavored tobacco (“didn’t taste good”, “may be a little hard for less experienced smokers”); however, some product reviews from WP aficionados are more positive (“This is a blend to be sipped and enjoyed slowly”), suggesting that current WP dependence level may be an important factor in the role of flavors.¹⁶

The overall aim of the current study is to determine if flavorings contribute to the initiation and maintenance (i.e., abuse liability) of WP smoking and also influence how a WP is smoked (i.e., smoking topography), which has implications for both risk of dependence but also smokers’ level of exposure to tobacco-related toxicants. Using a randomized crossover-design, 76 current WP smokers (38 low dependent, 38 high dependent) will complete four counterbalanced WP smoking sessions (preferred flavored-sweetened, preferred flavored-very low sweetened, unflavored-sweetened, unflavored-very low sweetened) that are preceded by 12 hours of tobacco/nicotine abstinence. Sessions will be separated by a standard 48-hour washout period.

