a specified interval (e.g. 1.5 +/- 0.2 lpm at 5 cm H₂O) will be retained for the study. This will assure that WPs used throughout the study are research qualified, while constructed of materials typical of what is used in the natural environment. All aspects of the WP apparatus will be held constant (water level, type of foil, disposable mouthpieces, and hoses). In every session, the waterpipe hose will be tipped with a new, sterile, disposable mouthpiece. Participants accompanying the index participant, will smoke from a second Mya Saray WP.

Charcoal: We will use self-lighting charcoal briquettes. Each piece of charcoal will be pre-weighed and will be placed on top of the foil. Tobacco: For the flavored-sweetened WP smoking session, participants will be able to choose their preferred flavor from a selection of the most popular Nakhla brand flavors that we will keep on hand to ensure availability. For the unflavored-sweetened session, participants will be provided Nakhla Zaghloul and for the flavored-very low sweetened and unflavored-very low sweetened session, the German version of Nakhla Shisha. Nakhla was chosen because it is a popular brand and is one of the few that has a flavored, unflavored-sweetened, flavored-very low sweetened and unflavored-very low sweetened tobacco product.

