WP Smoking Session Procedures: After completing the initial screening over the phone or online, participants will be informed of the study procedures and invited to the lab to complete the four WP smoking sessions. To ensure 12-hr abstinence, upon their arrival at the lab, participants will perform exhaled carbon monoxide testing (eCO<20ppm) and confirm that they have not used any nicotine/tobacco/marijuana products over the last 12 hours. Pregnancy exclusion will also be confirmed with a urine test (n.b.: pregnancy tests will be completed at each visit throughout the study). Along with a member of the study staff, the participant will review informed consent to ensure they understand their rights as a participant. Participants will be randomized and complete study procedures in self-selected dyads. The sessions will be counterbalanced and include: 1) smoking preferred flavored-sweetened WP tobacco 2) smoking unflavored-sweetened WP Tobacco and 3) smoking preferred flavored-very low sweetened WP tobacco and 4) smoking unflavored-very low sweetened WP tobacco. Participants will complete all four study visits in the laboratory. Pre-session abstinence from tobacco for at least 12 hours will be mandatory for all participants. Abstinence will be confirmed via participant self-report and an exhaled carbon monoxide monitor (< 20 ppm) for tobacco use. Participant dyads will first complete a 10-minute puffing session separated by 30-second intervals with the prepared hookah and then smoke *ad libitum* for up to 1 hour. This procedure will be completed for all visits. Participants will also complete a minimum 48-hour washout period between sessions.

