Data Analytic Plan: Data will be summarized using mean (SD). Both overall and stratified (by dependence level) statistics will be reported. For Aim 1, we will use linear mixed effects models (with a random subject effect) to assess the main effect of flavor on total volume of smoke inhaled, abuse liability score, nicotine and CO exposure levels. In addition, period and carryover effects will be considered in the model. All pairwise comparisons for the main effect of flavor will be conducted and Bonferroni-adjusted p-values reported. For Aim 2, we will further include dependence level (high vs. low) and its interaction with flavoring in the linear mixed effects models (as in Aim 1) for outcomes including total volume of smoke inhaled, interest in continued WP use, abuse liability score, and nicotine and CO exposure levels. If the interaction term is significant, flavoring group differences in the outcome for high and low dependence subjects will be compared using contrasts, again adjusting for multiple comparisons with Bonferroni's method. Data will be transformed as appropriate. Missing data will not be imputed and likelihood based linear mixed models will yield valid statistical inference under missing at random (MAR) and ignorable missing mechanism assumptions. A two-sided p-value of <0.05 defines statistical significance. The SAS software (v9.3, Cary, NC) will be used for all data analyses.

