Involvement and Design: Participants' eligibility will be determined over the phone or online using a screener and a pregnancy test will be completed at the initial visit to ensure that the participant is not pregnant. Those who are eligible and willing to participate will be invited to sign informed consent and complete their baseline visit. Enrolled WP smokers will complete four, 2-hr long counterbalanced WP smoking sessions that are preceded by 12 hours of overnight tobacco abstinence, biochemically verified by exhaled carbon monoxide (eCO<20ppm). Sessions will be separated by a standard 48-hour washout period. Participants will first complete a controlled 10-minute puffing session separated by 30-second intervals with the prepared hookah and then smoke ad libitum. The WP puff topography device will discretely record smoking behavior throughout the session, including puff duration, number of puffs, puff volume, and time between puffs. Blood samples (15ml per sample), eCO, and self-report measures of craving and withdrawal will be recorded immediately before and after the smoking session with two blood samples (less than 10mL) collected during the 10-minute puffing session. Self-report measures of abuse liability, as well as interest and willingness to continue to use the WP product just smoked will be assessed within 5 minutes after completing the smoking session.

Sources of Materials

All data collection will follow HIPAA guidelines. Data will be collected directly from the participant by a research assistant. Data will include participant responses to computer-based survey questionnaires and collected blood and breath samples.

Access to Identifiable Information and Data Storage: Only research assistants who have completed training in the ethical conduct of research and the study PI ([name]) will have access to individually identifiable private information about human subjects. All data will be treated as confidential and will never be stored or reported in association with identifying information. In the presence of hard copies of signed informed consent,

IRB NUMBER:

7117

IRB APPROVAL DATE:

12/18/2017

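### Sessions run in self-selected dyads, but the planned model treats partners as independent; if both partners are analysed, inference should be clustered by dyad

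*Combined protocol and SAP*

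**What the plan says.** In the Approach, WP Smoking Session Procedures states: "Participants will be randomized and complete study procedures in self-selected dyads". It continues: "Participant dyads will first complete a 10-minute puffing session separated by 30-second intervals with the prepared hookah", followed by ad libitum smoking, and applies this to every visit.

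Three other places bear on who these people are:

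- WP Materials: "Participants accompanying the index participant, will smoke from a second Mya Saray WP".
- Specific Aims: "76 current WP smokers (38 low dependent, 38 high dependent) will complete four counterbalanced WP smoking sessions". It does not say whether companions are among the 76.
- Section 5.1, Involvement and Design, describes the same step without dyads: "Participants will first complete a controlled 10-minute puffing session".

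The Data Analytic Plan specifies "linear mixed effects models (with a random subject effect", and says that period and carryover will be considered. It has no dyad term and no clustered variance. For Aim 1, "All pairwise comparisons for the main effect of flavor will be conducted and Bonferroni-adjusted p-values reported"; four products give six pairs. For Aim 2, "If the interaction term is significant, flavoring group differences in the outcome for high and low dependence subjects will be compared using contrasts".

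Nothing in the text supplied says whether partners receive the same sequence, or how dyads relate to the dependence groups.

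**The concern.** A random subject effect makes two people independent once the fixed effects are in the model. Partners who choose each other and smoke together for up to an hour at four visits may not be independent. Two mechanisms matter. One is a deviation that both share in a given session. The other is a reaction to a product that both share.

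A dyad that simply smokes more than others at every visit is not the problem, because that effect is the same under all four products and drops out of each person's contrasts. The harm arises only when the product contrasts themselves are correlated between partners. Reported standard errors can then be too small or too large, depending on the allocation of sequences and the make-up of dyads. At stake are the level of the Aim 1 pairwise tests and the Aim 2 interaction test, and how far the stated power can be relied on.

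**Working it through.** **Inputs from Power and Data Analytic Plan.** SD 30 L; within-subject correlation rho 0.1 to 0.8; two-sided alpha 0.025; Aim 1 smaller difference 110 − 92 = 18 L with 60 users; Aim 2 difference 44 − 10 = 34 L (also 39 − 5 = 34 L) with 30 per group. Planned completers: 76. **Assumed:** tau, the fraction of within-subject variance shared by partners, at 0.1 to 0.5.

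**1. The plan's own power.** At rho 0.1 the variance of a within-person difference is v = 2 × 30² × (1 − 0.1) = 1620, so its SD is 40.25 L.

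- Aim 1, paired t, SE = √(1620/60), 59 df: 87.46%. The plan states more than 87.5%.
- Aim 2, two-sample t, SE = √(2 × 1620/30), 58 df: 83.1%. The plan states more than 83%.

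Both figures are therefore the independence values at the worst-case rho.

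**2. Effect of correlated contrasts.** With n people in n/2 dyads and partners' contrasts correlated at tau:

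- Aim 1: Var(mean contrast) = v(1 + tau)/n. The naive test uses v/n, so a nominal 0.025 test has true size 2[1 − Φ(2.241/√(1 + tau))] = 3.3, 4.1, 4.9 and 6.7% at tau 0.1, 0.2, 0.3 and 0.5.
- Aim 2: the variance of the group difference is multiplied by 1 + tau if every dyad is same-group, by 1 − tau if every dyad is mixed, and on average by 1 for an even mix.

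**3. Simulated error rates.** 38 dyads, complete data, a four-sequence Williams square (the plan names a 6×4 Williams design), a subject + period + product model with 222 residual df, and 20,000 trials per cell. Monte Carlo error is about 0.15 to 0.25 points.

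Aim 1 family-wise error of the six contrasts at 0.05/6 (%):

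| Setting | tau 0 | 0.1 | 0.2 | 0.3 | 0.5 |
|---|---|---|---|---|---|
| Shared sequence | 4.2 | 6.0 | 7.1 | 9.5 | 13.7 |
| Shared product reaction, independent sequences | 3.9 | 5.4 | 7.5 | 9.1 | 14.1 |
| Session-level correlation, independent sequences | 4.1 | 4.4 | 4.2 | 4.1 | 4.2 |
| Session-level correlation, sequences forced to differ | 4.3 | 3.9 | 3.2 | 2.7 | 2.1 |

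Aim 2 interaction test at 5%, shared sequence (%):

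| Dyads | tau 0 | 0.1 | 0.2 | 0.3 | 0.5 |
|---|---|---|---|---|---|
| All same-group | 5.1 | 7.0 | 9.3 | 11.5 | 16.7 |
| All mixed | 5.1 | 3.6 | 2.2 | 1.1 | 0.1 |
| Half and half | 5.2 | 5.1 | 5.3 | 5.1 | 4.9 |

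A shared product reaction with independent sequences gives a similar Aim 2 pattern: 15.7% same-group and 0.2% mixed at tau 0.5.

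**4. With dyad-clustered standard errors** (G/(G − 1) correction, dyad-level df): Aim 1 family-wise 4.2 to 4.9%, Aim 2 interaction 4.5 to 5.8%.

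**5. Power on dyad-level df.** Noncentral t, alpha 0.025, rho 0.1. Aim 1: SE = √(1620(1 + tau)/n) with n/2 − 1 df. Aim 2, same-group dyads: SE = √(4 × 1620(1 + tau)/n) with n/2 − 2 df.

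| | tau 0 | 0.1 | 0.2 | 0.3 | 0.5 |
|---|---|---|---|---|---|
| Aim 1, 60 users | 86% | 82% | 78% | 75% | 68% |
| Aim 1, 76 users | 94% | 91% | 88% | 86% | 80% |
| Aim 2, 38 vs 38 | 91% | 87% | 84% | 81% | 75% |

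At rho 0.5 and tau 0.5, Aim 1 with 60 users still has 91.7%.

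**6. Index participants only.** There is no clustering. If the 76 include one companion each, 38 remain: Aim 1 SE = √(1620/38), 37 df, 66%; Aim 2 with 19 vs 19, 36 df, 61%.

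**The case against.** The strongest reply is that the harm is conditional and its size assumed. Inflation needs both partners in the analysis, correlated contrasts, and either a shared sequence or a shared product reaction. The documents give no tau. Separate waterpipes, individually preferred flavors and ad libitum smoking all suggest it may be small. At tau 0.1 the Aim 1 family-wise error is only 5.4 to 6.0%. This stands: a reader might infer that the primary test has been shown to fail, and the documents do not support that.

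Self-selected dyads need not be all same-group or all mixed, so the extreme Aim 2 figures are boundary cases. This also stands.

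A reader might infer that the stated power requires independence everywhere. It does so only near rho 0.1: with 60 users, rho 0.3 and tau 0.2, Aim 1 still has 88.2%. Nor is the trial shown to be underpowered. With 76 analysed at rho 0.1, the stated 87.5% survives to a tau of about 0.23 on dyad-level df.

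Section 5.1 is a human-subjects summary, so its silence on dyads is not a contradiction. WP Materials also calls the companions participants, which leans toward both being studied. The mention of an index participant still leaves the analysed set open. The protocol refers to a standard operating procedure that was not supplied, and part of the Approach is absent from the text reviewed; either may hold allocation details.

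What does not stand is that the subject effect already covers the problem. It absorbs a constant dyad level, not correlated product contrasts. Nor do spare participants help the error rate, since they restore power but not level.

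**Conclusion.** The point holds conditionally and should be fixed; confidence is medium. If both partners are analysed and share a sequence or a product reaction, the Aim 1 family-wise error is about 6, 9 and 14% at assumed tau 0.1, 0.3 and 0.5, against about 4% at zero. With independently allocated sequences and session-level correlation only, it stays at its usual level. The Aim 2 interaction is too liberal for all same-group dyads, conservative for all mixed dyads and near nominal for an even mix; the actual composition could fall anywhere between.

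With 76 people analysed, the main issue is whether the tests hold their level. If only index participants are analysed, the clustering concern disappears, but sample size becomes the issue should the 76 include companions.

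The simulated rates assume complete data and no carryover term. The plan expects 20% attrition, which would leave incomplete dyads, and it considers carryover; neither was tested.

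**What to change.** - Record a dyad ID. State whether both partners are analysed, how sequences are allocated within a dyad, and how dyads relate to the dependence groups.
- If both are analysed, keep the planned mixed model but base the Aim 1 contrasts and the Aim 2 interaction and contrasts on dyad-clustered standard errors, with a small-sample correction and dyad-level df. Random dyad-by-session and dyad-by-product effects together are an alternative. A plain dyad intercept does not help, and dyad-by-session alone misses a shared product reaction.
- State the power as conditional on no within-dyad correlation, or tabulate it over tau and rho.
- If only index participants are analysed, say so and say whether 94 recruited and 76 completers count them alone. If companions are included, restate the power.

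**Cost.** One recorded identifier and a few sentences. If tau is zero, clustering at rho 0.1 costs about 1 to 2 points of power: Aim 1 with 60 users goes from 87.5% to 85.8%, and Aim 2 with 30 vs 30 from 83.1% to 81.1%. The clustered Aim 2 test may be slightly liberal (up to 5.8%). No extra participants are needed if both partners are analysed.

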The Impact of Waterpipe Tobacco Flavors on Waterpipe Smoking Intentions, Perceptions, Patterns, and Toxicant Exposure

NCT03232827

Version Date: 12/18/2017

IRB NUMBER:
7117
IRB APPROVAL DATE:
12/18/2017

A. SPECIFIC AIMS

Waterpipe (WP) smoking in the US is on the rise and is beginning to overtake cigarettes as the most popular method of tobacco use among young adults.^{1,2} A potential reason for the appeal of WP tobacco is that it is almost exclusively flavored.³ Added sweeteners may also flavor the tobacco. The Family Smoking Prevention and Tobacco Control Act which banned flavors, except menthol, from cigarettes due to scientific evidence indicating that flavors increased youth initiation and maintained use among adults, does not currently apply to WP tobacco.⁴ As a result, WP tobacco is unregulated and comes in hundreds of flavors. In order to regulate WP tobacco effectively, the FDA requires clear scientific evidence to support regulations.⁴ **The present study will provide direct evidence to the FDA as to whether flavorings contribute to the initiation and maintenance of WP smoking, influence WP smoking patterns, and impact the uptake of toxicants.**

WP smoking involves inhaling smoke through a hose, causing air to be pulled over burning charcoal, heating the tobacco and producing smoke that travels through the waterpipe, the water, and finally the hose to the user.⁵ Mistakenly, WP users believe that the water filters out toxicants; however, WP users are exposed to the same toxicants that are present in combustible cigarette smoke, such as heavy metals, benzene, polycyclic aromatic hydrocarbons, tar, carbon monoxide, and nicotine, but often at *higher* levels.^{6,7} As such, **WP smoking is associated with many of the same negative health outcomes as combustible cigarette use such as cancer, lung disease, respiratory illness, and cardiovascular disease.**⁸

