Aim 1: To understand how flavorings impacts WP initiation, smoking behaviors, abuse liability, and exposure to tobacco-related toxicants. (H1a) *Flavored-sweetened WP tobacco will be associated with longer and more frequent puffing resulting in the greatest overall levels of smoke inhalation (mL of smoke inhaled), (H1b) highest abuse potential, and (H1c) greatest levels of exposure to nicotine and carbon monoxide (CO), followed by unflavored-sweetened WP, then flavored-very low sweetened and lastly unflavored-very low sweetened WP.* (H1d) *A majority of WP smokers will report having initiated WP smoking with flavoredsweetened tobacco and report flavoring as an important reason for trying WP.*

Aim 2: To understand whether level of WP dependence influences the impact of WP flavoring on smoking behaviors, intentions for continued use, abuse liability, and exposure to tobacco-related toxicants. Compared to high dependence users smoking unflavored WP tobacco, low dependence users will show greater declines in (H2a) puff frequency and duration resulting in lower levels of smoke inhalation, (H2b) intentions of continued use, (H2c) abuse liability, and (H2d) their exposure to nicotine and CO while smoking unflavored-sweetened and unflavored-unsweetened (greatest decline) vs. flavored-sweetened WP tobacco.

[figure not shown]

Our team is uniquely suited to conduct this investigation. Understanding how WP smokers and smoking would be influenced by a flavoring ban is critically important. This novel study addresses seven of the FDA's research priorities and will contribute knowledge urgently needed by the FDA and health officials to effectively regulate WP tobacco in a way that best serves public health.

SIGNIFICANCE

The rapidly growing popularity of WP smoking: While traditional tobacco product use (cigarettes, cigars, etc.) continues to decline, WP smoking is on the rise in the United States.^{1,17} From 2011 to 2014, current (past 30-day) cigarette use declined from 15.8% to 9.2% among high school students, while during the same period, current WP use increased from 4.1% to 9.4%.¹ Additionally, WP has overtaken cigarettes as the most frequently tried tobacco product among young adults (46.6%)¹⁸ and is frequently the first tobacco product ever tried (12.0%).² Recent estimates of current and ever WP use among adults also indicates an upward trend, with current and ever use rates currently at their highest (1.5% and 9.8%, respectively).¹⁹

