The extant WP research indicates that flavors have played a significant role in the spread of WP smoking.⁴⁷ In a nationally representative sample, 59% of WP smokers reported use of flavored tobacco, more than any other tobacco product.⁴³ Participants in qualitative research emphasize the importance of flavors in WP smoking stating, "I think it has to do with the flavor that got me to smoke it. It was a lot of variety" and "I like it, it was flavored and it was fun after a while".⁴⁸ Individuals also cite flavors as giving the impression that WP smoking in general is relatively harmless,⁴⁸ and that flavored WP tobacco is "healthier" than unflavored WP tobacco.⁴⁹ Anecdotal evidence of the importance of flavors in WP can be found in online reviews. Consumers indicate the significance of flavors in their reviews of unflavored shisha and state, "it was too strong" and "didn't taste good." One established user stated, "It is not for the new smokers," indicating the role of flavors in the initiation of WP smoking among naïve users. Making matters worse, emerging evidence indicates that WP use not only increases smokers' intentions and interest in using cigarettes,^{50,51} but longitudinal and prospective research shows that WP may also act as a gateway product to regular cigarette use.⁵²⁻⁵⁴ For these reasons, researchers and health officials have begun calling for a ban on flavored WP tobacco.³

Humectants, like glycerine, act as sweeteners and may enhance WP tobacco flavors. Regulators have limited the amount of glycerin (≤5%) in WP tobacco sold in Germany; substantially less than the levels sold in the U.S. (~25-50%).^{85,86} Unfortunately, Germany has not regulated the separate sale of bottles of WP-specific glycerin additive which are now sold alongside WP tobacco on German WP websites. The sale of these bottles

indicates the importance of glycerin to WP tobacco users. Thankfully, if the present study's hypotheses are supported, the Tobacco Control Act grants the FDA regulatory authority over these component products.

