Demographics: Measures will assess participant age, sex, marital status, ethnicity, employment status, occupation, years of education, and socioeconomic status.

Smoking Behavior Measure: WP smoking puff topography will be measured using a pressure transducer integrated into the WP hose, whereby inhalation-induced pressure changes are amplified, digitized, and sampled.⁶⁵ Software converts signals to airflow (ml/s) and integrates the flow data, producing measures of puff volume, total puff volume, puff number, and inter-puff-interval (IPI; i.e., amount of time between puffs).⁶⁵ Puff topography is a validated and sensitive measure of drug self-administration (i.e., a behavioral measure of abuse liability) that has been used for years in both the cigarette and WP smoking literature.⁷⁹ A smoker's puff topography is highly stable and associated with users' level of dependence and predicts their level of exposure to harmful tobacco-related toxicants.^{55,80-82}

Self-report Measures: WP Use History and Dependence: WP dependence will be measured using the *Lebanese Waterpipe Dependence Scale-11*.⁶⁶ This validated scale is correlated significantly with nicotine

exposure, CO, and WP use frequency.⁶⁶ We will also ask participants at what age they first used WP, if it was flavored/unflavored, importance of flavor to their desire to use WP, average number of WP sessions per month, quantity of tobacco smoked per typical WP session, usual brand, preferred flavor, number of WP quit attempts and other tobacco, nicotine and marijuana use. Abuse Liability of Product will be measured across several domains 1) experiences positive/negative drug effects, 2) behavioral-economic choice tasks, and 3) craving for and suppression of craving and withdrawal. An adapted version of the *Drug Effects/Liking*

| Table 1. Baseline and Outcome Measures | | | Baseline | Pre-Session | After 5min Puffing Session | After 10min Puffing Session | During Smoking Sessions | Post-Session |
|---|--|---|----------|-------------|----------------------------|-----------------------------|-------------------------|--------------|
| Self-Report Measures | | | | | | | | |
| Sociodemographic Measures | | X | | | | | | |
| Tobacco Products Quantity/Frequency | | X | | | | | | |
| WP Use History – AWS (Maziak et al 2016) | | X | | | | | | |
| Lebanon Waterpipe Dependence Scale-11 | | X | | | | | | |
| Hookah Readiness Rulers | | X | | | | | | |
| Hooked on Nicotine Checklist – Hookah | | X | | | | | | |

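### The listed use-history questions do not match the initiation hypothesis H1d on sweetness or on the reason for first trying, and the plan gives H1d no analysis

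*Combined protocol and SAP*

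**What the plan says.** Specific Aims, Aim 1 states H1d as: "A majority of WP smokers will report having initiated WP smoking with flavoredsweetened tobacco and report flavoring as an important reason for trying WP". It has two parts: what the first tobacco was, and whether flavor mattered in deciding to try.

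The baseline questions meant to inform it are described in the Self-report Measures section under WP Use History and Dependence. Participants are asked their age at first use and "if it was flavored/unflavored, importance of flavor to their desire to use WP", followed by items on current use. Table 1 also lists a baseline use-history instrument, the AWS, whose items are not shown.

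The Data Analytic Plan covers Aim 1 with linear mixed models for smoke volume, abuse liability, nicotine and CO, and says data will be summarized as mean (SD). It does not mention H1d. Predicted Results nevertheless expects the self-report measures to show that flavored-sweetened tobacco matters for initiation.

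On background exposure, Specific Aims says: "A potential reason for the appeal of WP tobacco is that it is almost exclusively flavored". It adds: "Unflavored WP tobacco is more difficult to find and purchase". The only percentage is in the Significance section: "59% of WP smokers reported use of flavored tobacco, more than any other tobacco product".

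**The concern.** Flavor and sweetness are separate factors in this trial: the four sessions cross them. The predicted ranking even places unflavored-sweetened tobacco above flavored-very low sweetened tobacco. A flavored/unflavored answer about the first product therefore covers only half of the product that H1d names. Likewise, how much flavor adds to someone's desire to use waterpipe is a different question from why that person first tried it, and an established user could answer the two differently.

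There is also an interpretive problem with the first part. If nearly all available product is flavored, most people will have started on flavored product whether or not flavor drew them in.

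The protocol promises the regulator direct evidence on initiation, and everyone enrolled must have smoked waterpipe for at least 6 months, so the sessions cannot observe first use. If H1d is answered from items that do not measure it, with no stated denominator or summary, its conclusion on initiation will not follow from the data. Questions not asked at baseline cannot be recovered at analysis.

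**Working it through.** **1. Hypothesis against listed items.**

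| What H1d needs | Listed item | Match |
|---|---|---|
| First tobacco flavored | Flavored/unflavored at first use | Yes |
| First tobacco sweetened | None | No |
| Flavor important in deciding to try | Importance of flavor to the desire to use | Not as described |
| Analysis of a proportion | None; mixed models for other outcomes, mean (SD) summaries | No |

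**2. Denominators.** The plan gives no sample size, threshold or test for H1d, so there is no figure to reproduce. The Participants section gives 94 recruited and 76 completing, with 20% attrition: 94 × 0.80 = 75.2, and 76 / 0.80 = 95, so the two agree to within rounding. Either could be the H1d denominator.

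**3. How informative is a majority on the first part?** Let X be the number who started on flavored tobacco, binomial with n participants and share p. P(X ≥ r) is the sum over k from r to n of C(n,k) p^k (1−p)^(n−k). A raw majority needs r = 39 of 76 or 48 of 94. For the exact 95% lower limit to exceed 50%, r must be at least 48 of 76 (48/76 = 63%) or 57 of 94 (57/94 = 61%).

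| p | n = 76, raw majority | n = 76, lower limit > 50% | n = 94, raw majority | n = 94, lower limit > 50% |
|---|---|---|---|---|
| 0.59 (documents) | 0.93 | 0.27 | 0.95 | 0.42 |
| 0.70 (assumed) | > 0.999 | 0.92 | > 0.999 | 0.98 |
| 0.90 (assumed) | about 1 | about 1 | about 1 | about 1 |

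The 59% is reported use among smokers. It is neither a market share nor the share starting on flavored product, and stands in here because it is the only number given. The 0.70 and 0.90 rows are assumed readings of the statement that product is almost exclusively flavored.

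**4. Both parts together.** Let a be the share starting on flavored tobacco (standing in for flavored-sweetened) and b the share of those starters who call flavor important in trying. The joint share is a × b. With n = 76 and r = 39:

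| a (assumed) | b (assumed) | a × b | P(joint majority) |
|---|---|---|---|
| 0.95 | 0.50 | 0.475 | 0.29 |
| 0.95 | 0.60 | 0.570 | 0.87 |
| 0.95 | 0.80 | 0.760 | about 1 |
| 0.90 | 0.50 | 0.450 | 0.16 |
| 0.90 | 0.60 | 0.540 | 0.72 |

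For an expected joint share of 50%, b must be 0.5/a: 0.5/0.95 = 0.53, or 0.5/0.59 = 0.85 at the documents' figure. Even with almost everyone starting on flavored tobacco, the combined hypothesis turns on the reason-for-trying answer, which the listed items do not clearly collect.

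**The case against.** The best defense is that H1d is a modest, descriptive sub-hypothesis. It is worded as what smokers will report, and no power or test is claimed for it. The protocol lists question topics, not verbatim wording; the importance item directly follows the first-use items and may be shorthand for a question about trying. The AWS is not reproduced and may hold the missing questions. On sweetness, the Significance section puts U.S. tobacco at about 25-50% glycerin against 5% or less in Germany, so for U.S. starters flavored probably meant sweetened, and many may not recall the difference.

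Much of this stands. It limits what can be claimed and lowers the weight of the point. It does not supply an analysis for H1d, and the glycerin argument is inference, not measurement.

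A reader might go further in three ways that the documents do not support:

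- **That H1d cannot be tested at all.** The flavored-start element can be described from the listed item, and the AWS content is unknown.
- **That H1d is met by market share alone.** Market share bears only on the first part; at an assumed 95% flavored share the joint majority has probability 0.29 if half name flavor. Even for the first part, at 59% a lower limit above 50% is reached with probability only 0.27 (76) or 0.42 (94).
- **That H1d is the only evidence on initiation.** The overall aim in Specific Aims ties initiation and maintenance together under abuse liability, which the randomized sessions compare. That inference in established smokers can be debated, but the plan does rely on it.

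**Conclusion.** The point holds in a limited form. The listed items do not record sweetness of the first product and, as described, ask about the desire to use waterpipe instead of the reason for first trying it. No analysis of H1d is specified. A raw majority starting on flavored tobacco would be likely from background use alone (0.93 to 0.95 at 59%), so it says little about flavor's role; the reason-for-trying part is not subject to that limit.

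This rests on reading a majority as more than 50%, on taking the listed topics as the content of the questions, and on using 59% as a proxy for the starting share. The shares of 70%, 90% and 95%, and the shares naming flavor, are illustrative. The binomial figures treat participants as independent; because they attend in self-selected dyads, whose members may have started together, the true uncertainty could be somewhat larger.

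H1d is secondary and descriptive. The primary outcome, total smoke inhaled, and the randomized comparisons are unaffected.

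**What to change.** First check the AWS. If it already asks about sweetness of the first product and flavor in the decision to try, cite those items against H1d. If not, add two items to the computer-based baseline questionnaire:

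- whether the first waterpipe tobacco was sweetened, with a do-not-know option;
- how important flavor was in deciding to try waterpipe the first time, with the response level that counts as important fixed in advance.

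In the Data Analytic Plan, state the denominator and report each part of H1d, and their combination, as proportions with exact 95% confidence intervals. Say how do-not-know answers are counted. Describe H1d as recalled, descriptive evidence from continuing users, and avoid reading a majority of flavored starts as evidence that flavor caused initiation.

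The cost is two more questions and a few sentences of analysis text. The main downside is that recall of sweetness may be poor, so that item may return many do-not-know answers.
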